The general study enrollment and investigational plan for Year # 1 (2020) and Year # 2 (2021) is illustrated and outlined in Figure 1 and Figure 2 respectively. Details regarding each individual study visit are illustrated and outlined in Figures 3-7. The study visits and details regarding each visit are further detailed in section 10 “Study Visits”.

The study PI and other investigators will be blinded to the allocation of participants to either carnosine or placebo. The participants will also be blinded to their allocation. The Randomization Committee (RC) will be in possession of the randomization key so that accurate unblinding of the randomization assignment may be identified in the event of a medical or other Carnosine NEAT Trial Protocol
Version Date 5-14-2020

emergency. The RC will consist of four individuals: the pharmacist compounding the supplement ([name]), the study physician ([name]), a member of the UofL Clinical Trials Unit, and the study biostatistician ([name]). Study supplements (carnosine or placebo) will be prepackaged into punch cards and marked with letters "A" or "B". The contents of series "A" or "B" will be part of the blinded randomization and will be known only to the RC. The study supplements will be directly shipped, stored and handled by the UofL CTU.

An initial screening (Visit # 1) of potential / interested participants will be conducted to identify eligible candidates based on eligibility criteria established *a priori*. Eligible candidates will be invited to a complete baseline assessment (Visit # 2). Randomization and allocation will occur between Visit # 1 and Visit # 2. Participants invited for Visit # 2 will already be randomized into one of the two study groups (carnosine or placebo). Participants from both study groups will be followed up at 6 weeks (Visit # 3) and 12 weeks (Visit # 4). Relevant and extensive data for primary and secondary endpoints will be collected at Visit # 2 through Visit # 4. The data collected throughout all visits (# 1 through # 4) may be used to generate preliminary data for future studies.

Visit # 1 will focus on consenting the participant for the entire study, collect contact/demographic information, and collect a urine sample. Safety assessments will be conducted at Visit # 3 and Visit # 4. Participants may be contacted for up to 12 months after enrollment via phone/email/mail for safety, adverse events, and or general follow up questions.

Study Endpoints

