Due to the prolonged intervention period (12 weeks), two follow-up visits and the inconvenience of taking multiple oral capsules daily, we anticipate a 40% attrition from screening (Visit # 1) through 12-week follow-up (Visit # 4). Therefore, we have established a goal of stratified identification of a total of 400 participants (1:1) at screening (Visit # 1). We anticipate that with a conservative estimate of 60% retention, 120 participants in each group (supplementation, placebo) will complete the entire study.

Multiple Testing Issue

Type I error correction in the context of an early phase clinical trial that performs multiple tests can serve to protect the study interpretation against Type I error inflation. However, the use of corrections for multiple comparisons in “proof-of-concept-studies” is problematic. At this investigational level, tight control of the overall family-wise Type I error rate would increase the likelihood that the investigators would miss a finding of potential importance by attributing it to chance simply because the p-value is large. The study investigators have, in this protocol, attempted to balance the need to control the number of evaluations with the need to identify new effects by not incorporating a multiplicity correction. The primary outcomes measures will be declared significant for alpha <0.01. There will not be any adjustments for secondary outcome measures and will be declared significant at alpha <0.05.

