All participants enrolled in this clinical trial will be identified as males or females, age 22-65, living within 30 miles radius of Louisville metropolitan area, and with carnosine levels less than the median of local population. After being identified (from existing database, from clinics, flyers, or other routes), potential participants will be approached by one of the investigators or research coordinators. The information provided to the potential participant is included in the informed consent. The informed consent will provide information regarding PM_{2.5} pollution, prevalence of PM_{2.5} pollution in the study area, synthesis and natural role of carnosine in the body, natural and supplemental sources of carnosine, cornstarch (constituent of placebo), and will include information regarding possible risks of participation.

Randomization

Eligible participants identified from Screening (Visit # 1) will be randomized in to supplement or placebo groups by 1:1 distribution. Randomization will be performed in accordance with written standard operating procedures by personnel that are not involved in the selection, screening, or enrollment of subjects and blinded as to study documentation. Randomization to supplement assignment will be conducted using a web access database created and maintained by the Randomization Unit. After the investigator or research coordinator verifies that screening testing is complete and the inclusion and exclusion criteria for the study have been satisfied, an un-blinded member of the Randomization Unit will have secured access to the participant's supplement assignment. The participant will be randomized a minimum of 2 days before the scheduled date of the baseline assessment (Visit # 2) to arrange for the timely availability of the study supplement. See Manual of Operations for details

Stopping Early or Withdrawal from the Study

Monitoring rules and statistical boundaries for adverse outcomes are further detailed in Section 15 "Data and Safety Monitoring Board". Below is the outline for recusal or withdrawal of participant from the study due to a non-health / safety related reason.

[figure not shown]
Participants that have consumed study supplement for at least 4 weeks during the duration of the study period, but missed taking the study supplement for no more than 1 week during the study period will still be followed if feasible, and included in intent to treat analysis.

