Participants that withdraw from the study before Follow-Up # 1 (Visit # 3) or do not complete Visit # 3 will be considered lost to follow-up. Existing data of these participants will be retained for further analysis.

Screen Failure

Candidates are considered screen failures when they meet one of the following criteria after signing consent:

1. Screening (Visit # 1) data reveals that the candidate is ineligible
OR

2. Candidate withdraws and does not complete Baseline Assessment (Visit # 2)

Discontinued

Participants are considered discontinued when they meet one or more of the following criteria:

1. Participant withdraws consent after being randomized
OR
2. Participant withdraws consent after completion of Baseline Assessment (Visit # 2)
OR
3. Participant fails to follow study supplement regimen
OR
4. Participant is unable to fulfill the inclusion/exclusion criteria during the study
OR
5. Participant refuses/is unable to provide critical data at follow-up visits as deemed necessary by the investigator
OR
6. Participant is withdrawn after randomization by investigator for reasons that may compromise completion of the study

Medical or Health Concerns

Participants will be instructed that in an event of an acute health concern (related or unrelated to the study supplement), they should immediately discontinue the study supplement and seek medical attention from a licensed healthcare provider. Participants will be provided with a study identification card. This card will contain the following information: name of the study, name of study institution, a statement to the effect of *“each capsule may contain 0.5 grams of L-Carnosine or 0.5 grams of cornstarch”*, method of contacting the study physician, and a method of contacting the study coordinator.

Participants may be able to re-start supplement regimen and continue the randomization after detailed discussions with the study physician. The study physician may seek advisement from the DSMB on these matters.

Compensation

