This questionnaire will assess participant’s dietary and exercise habits and their possible impacts on study supplement intake and processing throughout the study period. It will be administered by a research team member at baseline assessment (Visit # 2), Follow-Up # 1 (Visit # 3) and Follow-Up # 2 (Visit # 4).

Storage, Genetic Testing, and Future Use of Biospecimens

Blood and urine biospecimens collected during the study (detailed in Section 8 “Investigational Plan” and Appendix A) will be processed to be stored for long period. Majority samples will be processed, aliquoted, labeled, cataloged and immediately stored in -80C freezers in the Envirome Institute’s research laboratories located on the 2nd or 3rd floors of the Cardiovascular Innovation Institute ([name]).

Samples will be used to test for current hypothesis / endpoints and or generation of preliminary data for future studies. Samples may be used to genetic testing. These collected samples will be used for research purposes only. Samples will be stored without personal identifying

information, and will be shared with approved researchers who will conduct studies to improve the scientific knowledge including but not limited to environmental pollution and cardiovascular diseases. Samples will be retained for as long as possible.

Follow-Up Evaluations

Follow-Up Windows

The timeline for follow-up will begin on the day of baseline assessment (Visit # 2). The time windows for each of the subsequent follow-up visits will be as follows:

1. Follow-Up # 1 (Visit # 3) will be 6 weeks (6 weeks \pm 1 week post initiation of study supplement)
2. Follow-Up # 2 (Visit # 4) will be 12 weeks (11 weeks \pm 1 week post initiation of study supplement)
3. The 12 month safety check (via phone / email / mailed paper survey) will occur between 4 months and 12 months post completion of study supplement.

Scheduling and Lost to Follow-Up

Randomized participants will be followed for efficacy for 12 weeks and for safety up to one year (12 months). Participants will be considered lost to follow-up after 3 consecutive failed telephone/email contacts AND one certified letter returned to the site. Contact attempts will be documented in the participant's study chart.

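### Two definitions of lost to follow-up conflict, and adverse events in participants who stop before Visit 3 may be under-ascertained

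*Combined protocol and SAP*

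**What the plan says.** **Section 9, Stopping Early or Withdrawal from the Study.** Participants who "withdraw from the study before Follow-Up # 1 (Visit # 3) or do not complete Visit # 3 will be considered lost to follow-up". The next sentence adds: "Existing data of these participants will be retained for further analysis". The outline opens by stating its scope: "Below is the outline for recusal or withdrawal of participant from the study due to a non-health / safety related reason". Just before the rule, the same outline commits to continued follow-up, where feasible, for those who took the supplement for at least 4 weeks and missed no more than 1 week.

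**Section 12, Scheduling and Lost to Follow-Up.** "Participants will be considered lost to follow-up after 3 consecutive failed telephone/email contacts AND one certified letter returned to the site". The sentence before it has randomized participants followed for 12 weeks for efficacy and up to one year for safety.

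**Section 9, Medical or Health Concerns.** Participants with an acute health concern are told that "they should immediately discontinue the study supplement and seek medical attention from a licensed healthcare provider". The subsection continues: "Participants may be able to re-start supplement regimen and continue the randomization after detailed discussions with the study physician".

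**Scheduled safety checks.** Section 8 (Study Design): "Safety assessments will be conducted at Visit # 3 and Visit # 4". Section 10 puts Visit 3 at 5 to 7 weeks after the first capsule. The procedure schedules in Sections 12 and 18 mark adverse-event checks at Visit 3, Visit 4 and the 4-12 month contact only. In Section 10, that last contact asks about events after the intervention ended.

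**The concern.** Site staff cannot apply both definitions. Under Section 12 a participant stays in follow-up until contact attempts have failed. Under Section 9 the same participant can be closed as lost because one visit was missed, and no contact attempt is mentioned.

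The timing makes this a safety question. The reactions that the plan names (stomach upset, a fall in blood pressure, low blood sugar) could plausibly appear soon after the first capsules, and no check is scheduled until Visit 3. Those reactions are also holding criteria in Section 14, each measured against total enrolment. A missed event lowers the numerator and leaves the denominator unchanged. If carnosine caused early intolerance that went unreported, more events would be missed in that arm and the comparison would lean towards no harm. That last step is conditional: the documents give no evidence of such intolerance or of non-reporting.

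**Working it through.** **1. The plan's own figures.** Section 8 inflates 240 evaluable participants for 40% attrition: 240 / (1 − 0.40) = 400, which reproduces. Expected losses are 0.40 × 400 = 160. The Sample Size Recommendation counts this attrition from screening, so some of it may precede any capsule. No split by time or by reason is given. The number of dosed participants lost before Visit 3 therefore cannot be derived.

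**2. Timing.** Visit 3 is at 6 ± 1 weeks: 5 × 7 = day 35 to 7 × 7 = day 49, in a 12 × 7 = 84-day regimen.

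**3. The two definitions applied to the same participant.**

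| Participant | Section 9 | Section 12 |
|---|---|---|
| Leaves in week 2 for a non-health reason, still reachable | Lost | Not lost |
| Misses Visit 3, reason unknown, reachable | Lost by the literal wording | Not lost |
| Stops capsules for a reaction, attends Visit 3 | Not lost | Not lost |
| Stops capsules for a reaction, then misses Visit 3 | Outside the stated scope if the reason is known; lost by the literal wording if nobody asks | Not lost while reachable |

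The definitions disagree in rows 1 and 2, and in row 4 when the reason is not established.

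**4. Does another provision find the event in rows 2 and 4?**

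- Section 13 requires events to be monitored and reported from consent, but sets no contact before Visit 3. Its end point, 30 days after the participant completes the study, is undefined for someone who never completes.
- Section 14 gives events that halt the supplement the same reporting as serious events. Section 15 counts grade 3 or 4 events cumulatively. Both act on events already known.
- Section 16 asks participants to report listed symptoms at once, and Section 9 gives them a card with study contacts. Both rely on self-report.
- Section 8 allows contact for safety for up to 12 months after enrolment, but does not require it.
- The 4-12 month check looks forward from the end of the intervention. Whether that means the day capsules stopped or the end of the planned 12 weeks, the reaction that led to stopping came earlier.
- Retaining existing data adds no scheduled adverse-event data if no check has taken place.
- The express commitment to continued follow-up needs at least 4 weeks of use, so it does not cover someone who stops in week 1. Section 9 also classes failure to follow the regimen as discontinued, without saying what safety follow-up then applies.

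**5. Illustration of the effect on a holding criterion.** Let u be the share of affected participants whose event is never reported. This is an assumption; the documents give no value. Observed rate = true rate × (1 − u), so the true rate at which 20% is observed (0.20 × 400 = 80 participants at full randomization) is 20% / (1 − u):

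| u | True rate needed |
|---|---|
| 10% | 22.2% |
| 20% | 25.0% |
| 40% | 33.3% |

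**The case against.** The strongest reply is that the plan already protects safety follow-up. The Section 9 outline is limited to reasons unrelated to health or safety, and safety stops have their own subsection. Section 12 promises up to a year of safety follow-up without restricting it to completers. Section 10 has adverse events assessed through 12 months after the supplement is stopped, and it keeps a separate status for people lost to safety follow-up. The Section 9 label therefore need not end safety follow-up. Unscheduled events have several reporting routes, and the gastrointestinal, blood pressure and blood sugar reactions are on the list for serious-event reporting.

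Most of this stands, and it rules out two stronger readings.

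- A reader might infer that the instruction to stop capsules for a health concern itself makes a participant lost to follow-up. It does not. Stopping the supplement is not withdrawing from the study, the subsection allows a restart, and the outline's scope excludes health reasons. The participant would also have to miss Visit 3 without the reason being established.
- A reader might set the 160 expected losses against the 80-participant holding level and conclude that early reactions go uncounted. The losses are from all causes, are counted from screening and are undated. Each listed holding criterion counts one type of event. A dropout is not a hidden reaction.

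The reply does not remove the conflict between definitions. Nor does it supply an active enquiry for a dosed participant who misses Visit 3: the general promises of follow-up come with no scheduled question about that person's first weeks.

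**Conclusion.** The point holds as a contradiction between two stated rules, together with a gap in active safety ascertainment before Visit 3. If the Section 9 rule is followed as written, a participant who took capsules can be closed with no one having asked about adverse events. Events in such participants may be under-ascertained in the holding-criteria and toxicity counts. The documents do not show that they go uncounted.

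The size cannot be computed, because neither an early-stop rate nor a reporting rate is given. Any bias between arms needs two further assumptions: more early intolerance on carnosine, and non-reporting of it. Confidence is medium, because Section 12's general promise could be read as overriding the Section 9 label. The sponsor should settle this by wording and not leave it to interpretation.

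**What to change.** - Remove the separate Section 9 rule and use the Section 12 definition of lost to follow-up throughout.
- State that every participant who took at least one capsule stays in the Visit 3, Visit 4 and 4-12 month adverse-event checks, whether or not still taking capsules and subject to withdrawal of consent. For those who do not attend, use the phone, email or mail route that the plan already has.
- For these participants, word the adverse-event question to cover the whole period since the first capsule.
- State that the discontinued category does not by itself end safety follow-up.

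The cost is protocol wording and some extra calls or emails by existing coordinators. No visit or procedure is added, and no dose, restart or stopping rule changes.

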10. STUDY VISITS

Screening (Visit # 1)

The screening period extends from the date informed consent is signed until the day of randomization (Figure 3). The screening window will not exceed 180 days prior to randomization.

The following activities will be carried out at screening:

1. Informed Consent (for entire study)
2. Blood and or Urine sample collection
3. Demographic data
4. Contact information
5. Prepaid \$25 VISA gift card

Participants may be excluded from the study if any of the above screening data collection is not completed or meets an exclusion criterion during the screening period. Data gathered from screening (Visit # 1) will be used to identify whether the candidate meets the enrollment criteria for the main study and whether they are eligible to be randomized. Eligible candidates will be invited to participate in the main study and subsequently randomized in a double blind fashion.

Baseline Assessment (Visit # 2)

Baseline assessment will occur after eligible candidates have been identified via screening (Visit # 1) (Figure 4). Participants attending the baseline assessment (Visit # 2) will already be randomized into carnosine or placebo group. Participants will be provided with the study supplement during this visit and they will start their dietary supplement regimen (carnosine or placebo) immediately on the day of baseline assessment. The following activities will be carried out at Baseline Assessment:

1. Update Demographics and Contact Information
2. Questionnaire data on Medical History, Medications, Exposure to Environmental Pollution, Sleep, Diet, Exercise, Tobacco, and Women's Health
3. Blood sample collection (~3 tablespoons or ~45ml)
4. Urine sample collection (~2 tablespoons or ~30ml)
5. Arterial stiffness test (SphygmoCor)
6. Physical strength test (hand grip test, step test, calf raise test)
7. Provide 8 weeks of study dietary supplement capsules (carnosine or placebo)
8. Discuss schedule and related instructions related to taking the study dietary supplement
9. Prepaid \$50 VISA gift card

Participants may be excluded from the study if any of the above data collection is not completed or meets an exclusion criterion during this period.

Follow-Up # 1 (Visit # 3)

Follow-Up # 1 will occur ~6 weeks after initiation of study supplement at the baseline assessment (Visit # 2) (Figure 5). Participants attending follow-up # 1 (Visit # 3) will have already been taking the study supplement for at least 5 weeks and no more than 7 weeks (6 weeks \pm 1 from Visit # 2). The following activities will be carried out at Follow-Up # 1:

1. Update Demographics and Contact Information
2. Update Questionnaire data on Medical History, Medications, and Women's Health
3. Questionnaire data Exposure to Environmental Pollution, Sleep, Diet, Exercise, Tobacco
4. Blood sample collection (~3 tablespoons or ~45ml)
5. Urine sample collection (~2 tablespoons or ~30ml)
6. Arterial stiffness test (SphygmoCor)
7. Physical strength test (hand grip test, step test, calf raise test)
8. Review the participant's dietary supplement regimen and any instances of deviation in regimen (missed or over consumption).
9. Provide 4 more weeks of study dietary supplement capsules (carnosine or placebo)
10. Discuss any side-effects which may have occurred or may arise from study supplement. Discuss any health changes during the study period.
11. Prepaid \$75 VISA gift card

Participants may be excluded from the study if any of the above data collection is not completed or meets an exclusion criterion during this period.

Follow-Up # 2 (Visit # 4)

Follow-Up # 2 will occur ~12 weeks after initiation of study supplement at the baseline assessment (Visit # 2) (Figure 6). Participants attending follow-up # 2 (Visit # 4) will have already been taking the study supplement for at least 10 weeks and no more than 12 weeks (11 weeks \pm 1 from Visit # 2). The following activities will be carried out at Follow-Up # 2:

1. Update Demographics and Contact Information

2. Update Questionnaire data on Medical History, Medications, and Women's Health
3. Questionnaire data Exposure to Environmental Pollution, Sleep, Diet, Exercise, Tobacco
4. Blood sample collection (~3 tablespoons or ~45ml)
5. Urine sample collection (~2 tablespoons or ~30ml)
6. Arterial stiffness test (SphygmoCor)
7. Physical strength test (hand grip test, step test, calf raise test)
8. Review the participant's dietary supplement regimen and any instances of deviation in regimen (missed or over consumption).
9. Discuss any side-effects which may have occurred or may arise from study supplement.
Discuss any health changes during the study period.
10. Prepaid \$100 VISA gift card

Participants may be excluded from the study if any of the above data collection is not completed or meets an exclusion criterion during this period.

4 – 12 Month Safety Check (Visit # 5)

Although this interaction is termed as a “Visit”, it will not involve participants to physically be present. A follow-up email / phone call / mailed paper questionnaire will be conducted 4-12 months after the end of supplement intervention (Figure 7). This contact will focus on updating about any SAEs & medical / medication history changes since end of intervention:

1. Update Demographics and Contact Information
2. Questionnaire data on Medical / Medications History since end of intervention
3. Questionnaire data on adverse effects or SAEs since end of intervention.
4. No monetary compensation for this follow-up / check.

Participants will not be excluded from the study if any of the above data collection is not completed. Instead, they will be categorized as “lost to safety follow-up”.

Safety Evaluations during Study Visits

Adverse events will be assessed during Visit # 3 and Visit # 4 and through the 12 months after participants have stopped taking study supplement. The following will be documented in the adverse event reporting system:

1. **Local reactions:** diarrhea, stomach upset, tingling sensation in extremities, rash or itchiness, dry mouth, changes in appetite, feelings of tiredness, or vivid dreams.
2. **Systemic reactions:** fever, allergic reaction, anaphylaxis or any clinical untoward event that occurs within 30 days of beginning study supplement.
3. **Abnormal laboratory results** which are deemed clinically significant.
4. **Pregnancy and breast-feeding:** Currently, there is not enough reliable information about the safety of taking carnosine supplement during pregnancy or breast-feeding. Hence, participants/candidates who are currently pregnant or breast-feeding or plan to be pregnant/breast-feeding during the study period will be “discontinued” from the study.

5. **Low blood pressure:** Carnosine synthesized in the body has been found to decrease blood pressure via influencing the autonomic nervous system.⁴³ Hence, in theory, taking supplemental carnosine might lower blood pressure and or exacerbate lowering of blood pressure in people taking antihypertensive medications. Hence, all participants taking blood pressure lowering medication will be cautioned for this interaction and advised that in case of an episode of low blood pressure to discontinue study supplement and immediately seek medical attention from a licensed healthcare provider.
6. **Low blood sugar:** Carnosine synthesized in the body has been found to decrease blood sugar via influencing the autonomic nervous system.⁴³ Hence, in theory, taking supplemental carnosine might lower blood sugar and or exacerbate lowering of blood sugar in people taking blood sugar lowering medications. Hence, all participants taking blood sugar lowering medication will be cautioned for this interaction and advised that in case of an episode of low blood sugar to discontinue study supplement and immediately seek medical attention from a licensed healthcare provider.

Participants will be advised to continue / discontinue after a review by the study physician and the DSMB.

[figure not shown]

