Hospitalization does not include rehabilitation facilities, hospice facilities, respite care (i.e., caregiver relief), skilled nursing facilities or homes, routine emergency room admissions, or same day surgeries (as outpatient/same day/ambulatory procedures). Hospitalization or prolongation of hospitalization in the absence of a precipitating, clinical AE/SAR is not in itself an SAE/SSAR.

Unanticipated Problems (UPs)

An UP is an incident, experience, or outcome that specifically causes increased risk to the study or to its participants which may be of medical or non-medical etiology, and meets the following criteria:

1. Unexpected (in terms of nature, severity, or frequency), given (a) the research procedures that are described in the protocol-related documents, such as the IRB-approved research protocol and informed consent document; and (b) the characteristics of the subject population being studied
2. Definitely, probably, or possibly related to participation in the research (i.e., there is a reasonable possibility that the incident, experience, or outcome may have been caused by the procedures or materials involved in the research); and
3. Suggests that the research places participants or others at a greater risk of harm (including physical, psychological, economic, or social harm) than was previously known or recognized
4. All UP reporting will follow the same guidelines as noted above for SAE/SSAR reporting, and must include a corrective action plan/measures to prevent recurrence.

Reporting by Principal Investigator

For all events (AE/SAR and SAE/SSAR), monitoring and reporting to the PI or EC begins at the time that the participant provides informed consent, which is obtained prior to the participant's participation in the study, i.e., prior to undergoing any study related procedure and/or receiving study supplement, through and including 30 calendar days after the subject completes the study. Events should be recorded on the Adverse Event electronic case report form (eCRF). Do not delay the initial reporting of an event in order to obtain resolution or follow up information.

For all events, the PI must pursue and obtain adequate information both to determine the severity and causality of the event. For events with a causal relationship to the study supplement, follow-up by the Investigator is required until the event or its sequelae resolve or stabilize at a level acceptable to the PI, who concurs with that assessment.

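### The protocol gives three conflicting adverse-event windows, and the only catch-all in the Section 10 list closes 30 days into a 12-week supplement

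*Combined protocol and SAP*

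**What the plan says.** Three statements set a period for adverse events.

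- **Section 10, Safety Evaluations during Study Visits, lead sentence.** Events are assessed at Visits 3 and 4 "and through the 12 months after participants have stopped taking study supplement".
- **Same subsection, item 2 of the list to be documented.** After naming fever, allergic reaction and anaphylaxis, the systemic-reactions item ends with "any clinical untoward event that occurs within 30 days of beginning study supplement". Items 1 and 3 to 6 (named local reactions, clinically significant laboratory results, pregnancy and breast-feeding, low blood pressure, low blood sugar) have no time limit.
- **Section 13, Reporting by Principal Investigator.** For all events, serious or not, "monitoring and reporting to the PI or EC begins at the time that the participant provides informed consent" and runs "through and including 30 calendar days after the subject completes the study". Events are recorded on the Adverse Event eCRF. The protocol does not say what counts as completing the study.

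Two other places bear on the point without setting a separate collection window. Section 12, Follow-Up Windows, puts the remote safety check "between 4 months and 12 months post completion of study supplement", which agrees with Section 10. Section 8, Study Design, says "Participants may be contacted for up to 12 months after enrollment", which permits contact but does not define what is collected.

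**The concern.** The supplement is taken daily for 12 weeks, yet the one list item able to capture an unlisted event stops at 30 days from the start. Chest pain on day 60, for example, matches no item on that list, although Section 13 would require it to be reported. At the other end, the remote safety check exists to collect adverse effects and serious events since the end of the intervention. On one natural reading of Section 13, it takes place after the reporting window has closed.

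At stake is the consistency of the safety counts. The 20% holding criteria in Section 14 and the grade 3 or 4 toxicity boundary in Section 15 both count events without naming a period. The semi-annual reports to the DSMB give total numbers of adverse and serious adverse events. If staff can follow different sections and record different events, those totals do not have one fixed meaning.

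**Working it through.** **Inputs.** Day 0 is the first dose, taken at Visit 2.

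- Supplementation: 12 consecutive weeks (Section 8), so 12 × 7 = 84 days. Section 15 supplies three 28-day boxes, 3 × 28 = 84, which agrees.
- Visit 3: 5 to 7 weeks (Section 10), so day 35 to 49. The schedule tables in Sections 12 and 18 show no adverse-event check before it.
- Visit 4: 10 to 12 weeks (Section 10), so day 70 to 84.
- Safety check: 4 to 12 months after supplement ends. Taking day 84 as the end and a month as 365.25/12 days, the earliest date is 84 + 121.75 = 205.75, about day 206. The latest is 84 + 365.25, about day 449.

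**Where each window ends.**

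| Source | Start | End |
|---|---|---|
| Section 10, item 2 catch-all | First dose | Day 30 |
| Section 10, lead sentence | Checks at Visits 3 and 4 | 84 + 365 = about day 449 |
| Section 13, if completion is Visit 4 | Consent | 70 + 30 = day 100, to 84 + 30 = day 114 |
| Section 13, if completion is the safety check | Consent | 206 + 30 = about day 236, to 449 + 30 = about day 479 |

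**Catch-all against exposure.** 84 − 30 = 54 days lie outside it, and 54/84 = 64%. It closes 35 − 30 = 5 days before the earliest permitted Visit 3.

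**Section 13 against the safety check.** If completion is Visit 4, the window closes by day 114 at the latest. The earliest safety check is then 206 − 114 = 92 days later. An event that began before the window closed but was first reported at the check might still qualify by onset date. Section 13 does not say whether onset or report date decides. Events that begin after the close are outside it on either reading.

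**Section 8.** Its 12 months run from enrollment, which could be several dates. Counted from randomization 2 days before baseline, they end on day 365 − 2 = 363. Counted from consent 180 days before that randomization, they end on day 365 − 182 = 183, before the earliest safety check. This is a reason to align the wording, but it is not a fourth window.

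**The case against.** The strongest reply is that Section 13 is the dedicated adverse-event section, is written for all events, starts at consent and covers the whole supplementation period. The list item in Section 10 could then be treated as an aside. That is a sensible way to read the protocol, but no clause gives Section 13 precedence, and it leaves the end date open because completion is undefined.

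Several other points against the concern stand:

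- The 30-day limit is in one of six items. Grammatically it may attach only to the catch-all phrase, leaving fever, allergic reaction and anaphylaxis untimed.
- At Visits 3 and 4 staff discuss side effects and any health changes during the study period, with no 30-day limit. The schedules place an adverse-event check at both visits and at the safety check.
- Section 16 also has participants assessed for adverse events at each follow-up visit, and asks them to report a fever at once.
- Stomach upset, low blood pressure and low blood sugar, which feature in the holding criteria, are untimed in Section 10.
- Both arms use the same text and staff are blinded, so no between-arm bias is shown. No efficacy endpoint is affected.

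A reader might infer that every systemic reaction in the last 54 days of supplementation goes undocumented, that events found at the safety check will not reach the eCRF, or that the protocol has four separate windows. The documents do not support these readings. Other sections ask about or record later events. The eCRF gap depends on what completion means. The Section 8 sentence is only permissive.

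**Conclusion.** The concern holds as an internal inconsistency. Three statements about the adverse-event period cannot all be the collection window, and nothing says which governs. Under Section 10 taken literally, an untoward event that matches no other item and occurs in the last 54 of 84 supplement days (64%) is not on the list to be documented, while Section 13 requires it. Under Section 13, the end of reporting moves from day 100 to 114 to about day 236 to 479, depending on whether completion means Visit 4 or the safety check.

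The 64% applies to the catch-all phrase, not to all adverse events. The day counts assume supplement stops on day 84. If it stopped at a day-70 Visit 4, the earliest safety check would be 70 + 121.75, about day 192, still after a Section 13 close on day 100. The documents give no event rates over time, so the number of events affected cannot be estimated. The finding is that the counts behind the holding criteria and toxicity boundary depend on the section followed. It is not that a known number of events will be lost.

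**What to change.** Reconcile Sections 10 and 13 into one stated start and end of adverse-event collection that applies to every event class and covers the whole supplementation period. Align the wording of Section 8 and Section 12 with it. Define study completion, and say whether onset date or report date decides if an event falls within the window. State whether events found at the 4-12 month safety check enter the eCRF, and whether they count toward the Section 14 holding criteria and the Section 15 toxicity boundary. The end date is for the sponsor to choose.

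The cost is protocol wording only. The visits and the remote contact are already scheduled, so no new data collection is needed.
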